SUMMARY OF STUDY RATIONALE	
Multiple Myeloma (MM) is a blood cancer of the plasma cells. Treatment for MM includes bortezomib and bortezomib combination chemotherapy which causes Chemotherapy-Induced Peripheral Neuropathy (CIPN) in approximately 30% of patients. CIPN is characterized by sensory symptoms including tingling, numbness, burning, weakness, pain, and aching in the hands and/or feet. Individuals with CIPN experience reduced quality of life (QOL) due to poor physical function, greater disability, falls, reduced functioning, and dose limiting or early discontinuation of anti-cancer treatment. Treatments for CIPN typically include concomitant medications, (e.g., gabapentin, duloxetine) yet these approaches have limited evidence to support clinical use, have side effects, and are not universally effective. Previous research suggests acupuncture is effective in treating CIPN in other populations with few side effects, yet the effect of acupuncture on CIPN among MM patients is poorly understood.

STUDY DESIGN	
This study is a randomized, controlled trial in which subjects will be assigned 2:1- 2 to acupuncture intervention to 1 standard subject care. Those assigned to acupuncture will receive a total of 12 sessions over approximately 10 weeks. During the first two weeks, acupuncture will occur twice per week and during weeks 3-10 acupuncture will occur once per week. All subjects will be assessed for sociodemographic and medical characteristics, neuropathy on a scale from 0=no neuropathy– 10=worst possible neuropathy, the FACT-GOG-NTX scale on CIPN symptoms, physical, social/family, emotional, and functional well-being, other specific symptoms, quality of life, and opioid and concomitant medication intake. Assessments will occur at Baseline, Midpoint, and Endpoint over the approximately 10 weeks subjects will be on study. Comparisons will be made between the intervention and control groups.

OBJECTIVES	
Primary Objective: To evaluate the effectiveness of acupuncture plus standard subject management versus standard subject management in terms of reduction of neuropathy in multiple myeloma subjects being actively treated with bortezomib diagnosed with CIPN or multiple myeloma subjects who have discontinued bortezomib within the past 12 months but continue to have CIPN (even if they have started new therapy that could cause neuropathy). Neuropathy will be subject reported using an 11-point scale from 0-No Neuropathy to 10-Worst Possible Neuropathy.
 
Secondary Objectives:
 
 • To compare subjects with and without acupuncture for the following symptoms assessed by the FACT-GOG-NTX questionnaire:

	
• Specific features of CIPN utilizing the NTX sub-scale (e.g. numbness, tingling)• Nausea• Sadness• Nervousness• Sleep quality• Lack of energy• Pain. 
• To compare subjects with and without acupuncture for the following symptoms assessed by an adaptation of the FACT-GOG-NTX questionnaire:
• Constipation• Dizziness• Dry mouth.• To compare Quality of Life in subjects with and without acupuncture using the CDC HRQoL-4 questionnaire.
--	--

Safety Objective:

- To summarize adverse events of special interest for subjects receiving acupuncture intervention

Exploratory Objectives:

To compare subjects with and without acupuncture for:

- Opioid use, defined by Morphine Equivalent Daily Dose (MEDD)¹
- Concomitant medication use, including gabapentin, duloxetine, pregabalin, etc.
- To evaluate whether there is a dose response based on the amount of acupuncture delivered, defined by the number of attended acupuncture sessions from 0 to 12 for those randomized to the acupuncture arm.
- To evaluate the effect of acupuncture expectancy for subjects receiving acupuncture intervention

KEY INCLUSION CRITERIA	
 • Age \geq 18 years at the time of consent • Subject has diagnosis of multiple myeloma (any stage) • Currently being treated with bortezomib or bortezomib-combination chemotherapy; also allowed are those subjects who have discontinued bortezomib within the past 12 months but continue to have CIPN (even if they have started new therapy that could cause neuropathy) • ECOG Performance status of 0-3 • Life expectancy of \geq 12 weeks • Subject reported Neuropathy score of \geq 2 • No planned hospital admission within the expected time frame of study participation. For potential participants with a transplant in their current MM treatment plan: Post-transplant subjects may enroll when recovered sufficiently from the transplant, i.e. platelets $>50 \times 10^3/\mu\text{L}$, ANC $> 0.5 \times 10^3/\mu\text{L}$, and ECOG performance status is 0-3.
KEY EXCLUSION CRITERIA	
 • Subjects with neuropathy pain as a result of any other cause other than chemotherapy • Subjects with needle phobia • Previous diagnosis of amyloidosis or POEMS syndrome • Documented local infection at or near the planned acupuncture sites (see Appendix A) • Subjects with metastatic involvement of the nervous system/active central nervous system disease • Plan to receive Healing Touch or Oncology Massage during study participation • Have received acupuncture within 30 days prior to enrollment
STATISTICAL CONSIDERATIONS	
This study is designed with a primary objective to evaluate the effectiveness of acupuncture versus standard subject management in terms of reduction of neuropathy in actively treated multiple myeloma subjects diagnosed with CIPN. A Fisher's Exact Test with a 20% two-sided significance level will have 80% power to detect the difference between a standard of care group proportion of 0.10 and a treatment group proportion of 0.35 when the sample sizes are 22 and 44, respectively.

NUMBER OF SUBJECTS	
66 evaluable (It is estimated that a total of 75 subjects may be enrolled to achieve 66 evaluable subjects)

SCHEMA

Recruitment of N=66 evaluable Multiple Myeloma (MM) patients currently treated with Bortezomib or Bortezomib-combination chemotherapy with chemo-induced peripheral neuropathy (CIPN); also allowed are those subjects who have discontinued bortezomib within the past 12 months but continue to have CIPN (even if they have started new therapy that could cause neuropathy)

1. BACKGROUND AND RATIONALE

1.1 Background

1.1.1 Multiple Myeloma (MM)

MM is a blood cancer of the plasma cells classified as a blood disorder. Plasma cells are white blood cells that produce antibodies to protect against disease and infection. Myeloma hinders the production of antibodies within the bone marrow which leads to reduced immune response and kidney damage. Myeloma also damages bone which leads to bone pain and fractures.²

1.1.2 Chemo- Induced Peripheral Neuropathy (CIPN)

First-line treatment for MM is usually bortezomib (Velcade®) or bortezomib combination chemotherapy.³⁻⁵ At Levine Cancer Institute, approximately 85% of MM patients receive bortezomib containing chemotherapy. Although chemotherapy is associated with improved survival, it is neurotoxic and causes CIPN in approximately 30% of patients.^{6,7} CIPN is characterized by sensory symptoms including tingling, numbness, burning, weakness, pain, aching in the hands and/or feet,⁸ and neuropathic pain in more severe cases.⁹ The pathophysiological mechanisms of CIPN are complex and multi-factorial which include oxidative stress, apoptotic mechanisms, altered calcium homeostasis, axon degeneration, membrane remodeling, and neuroinflammation.¹⁰ Bortezomib-induced peripheral neuropathy in MM patients usually presents within the first five cycles of treatment.¹¹

Depending on the severity of CIPN, the dose of bortezomib may be reduced or discontinued to avoid debilitating side-effects. Dose reductions and discontinuation of treatment negatively impact the treatment's ability to prolong life.¹¹ Individuals with CIPN experience reduced quality of life (QOL) due to poor physical function, greater disability, falls, and reduced functioning.¹²⁻¹⁵ CIPN may last for years past treatment and is sometimes permanent.¹⁶

1.1.3 Current Treatments for CIPN

There are no cures for CIPN; it can only be treated.¹⁷ Treatments for CIPN include concomitant medications which target various pathophysiological mechanisms. Pharmacologic options include anticonvulsants (e.g., gabapentin, (Neurontin®, Gralise®), antidepressants (e.g., duloxetine (Cymbalta®)), over-the-counter (e.g. aspirin, ibuprofen), prescription (e.g., celecoxib (Celebrex®)), non-steroidal anti-inflammatory drugs (NSAIDs), and opioids in severe cases unresponsive to other treatments. Topical agents (e.g., amitriptyline, lidocaine) applied to the skin are also options.^{18,19} These treatments, however, are not universally effective. Menthol and capsaicin can be used but¹⁸ have side effects and there is limited evidence to support their clinical use.⁶ Side effects of anticonvulsants include drowsiness and dizziness, and antidepressants are associated with dry mouth, nausea, drowsiness, dizziness, decreased appetite and constipation.²⁰ Nonpharmacologic options with varying levels of efficacy include neurostimulation, exercise, nonpharmacologic menthol and capsaicin topical agents, and

acupuncture.¹⁸ For patients open to integrative modalities to lessen CIPN symptoms, acupuncture is a promising intervention.

1.1.4 Acupuncture for CIPN in Multiple Myeloma

Acupuncture is a nonpharmacologic practice within Traditional Chinese Medicine that involves the insertion of thin needles at specific sites on the body, known as acupoints, to affect the body's physical function and induce a therapeutic response.²¹ Previous studies show promise for acupuncture's use for peripheral neuropathy in MM,²²⁻²⁵ however, sample sizes have been small and additional studies are needed.²⁶

In 2011, Bao and colleagues reported the first case study of a MM patient who experienced significantly reduced bortezomib-induced peripheral neuropathy (BIPN) after fourteen acupuncture treatments. The patient had significantly reduced neuropathic pain, less requirement for narcotics to treat pain, and improved physical function with minimal side effects.²⁷ Another case study by Mandıroğlu, Çevik, & Ayli (2014) found complete resolution from a BIPN pain score of eight to zero out of ten after six months of acupuncture without any side effects.

This was followed by a case series of five patients of the same population who all received immediate BIPN-related pain reduction after a single acupuncture treatment. Two of the three patients who had at least three acupuncture sessions experienced lasting pain relief and functional improvement after the last acupuncture session. There were no adverse effects.²³ The same author team then pursued a pilot study of twenty-seven MM patients with BIPN resistant to other medical interventions even after bortezomib had been discontinued. Neuropathic pain was significantly reduced and physical function was significantly improved after ten acupuncture sessions over ten weeks.²⁵ A feasibility study of nineteen MM patients with BIPN who were given twenty electroacupuncture sessions over nine weeks found significantly improved pain and physical functioning including walking, buttoning buttons and postural stability.²⁴ A systematic review and meta-analysis of the efficacy of acupuncture for CIPN found that acupuncture can relieve CIPN pain and functional limitations, which warrants larger scale studies.²⁸

1.1.5 Acupuncture for Quality of Life and Other Symptoms

While primarily targeting CIPN, other QOL-related symptoms may also improve with acupuncture. Evidence suggests depression,^{29,30} fatigue,³¹⁻³³ constipation,³⁴ nausea, vomiting,^{35,36} sleep disturbance,^{37,38} general pain,³⁹⁻⁴² and dry mouth^{43,44} are reduced. Health-related quality of life (HRQOL) can be measured with the validated CDC HRQOL-4.^{45,46} Studies indicate that those who expect that acupuncture will be beneficial tend to have better outcomes than those who do not believe acupuncture will have a positive effect. The expectancy effect can be controlled for using the validated Acupuncture Expectancy Scale.⁴⁷

1.1.6 Acupuncture as Potentially Opioid and Concomitant Medication-Sparing

For some patients, the therapeutic benefits of acupuncture may lead to less need for pharmacologic management of symptoms. In a retrospective chart review of military patients,

those who experienced acupuncture had fewer opioid prescriptions and had better symptom control, ability to function and improved sense of well-being. Opioid prescriptions decreased 45%, muscle relaxants 34%, NSAIDs 43%, and benzodiazepines 14%.⁴⁸ In a small study of 35 chronic pain patients, electroacupuncture was associated with a more rapid reduction in opioid-like medications compared to sham electroacupuncture.⁴⁹

1.1.7 Safety and Patient Acceptability of Acupuncture

Acupuncture is a low-cost treatment option^{50,51} that is in-demand by patients.^{52,53} It generally has very few adverse events (AEs) and is considered safe when provided by qualified acupuncturists. AEs can include minor bleeding, pain and/or bruising at the needling site, fatigue, sweating, and faintness (also called “needle shock”).⁵⁴ Serious AEs including infections, blood-borne diseases, and internal organ or tissue injury are rare.⁵⁵ In a study of 65,000 treatments over six years in Japan, only 94 minor AEs were reported.⁵⁶ In a study of over 760,000 treatments among 97,733 patients in Germany, there were 6 cases of potentially serious AEs including worsened depression, hypertensive crisis, asthma attack, vasovagal reaction, and pneumothorax.⁵⁷ Cancer patients are at higher risk for AEs than non-oncology patients. AE risk can be reduced by employing oncology-trained acupuncturists, following Clean Needling Technique (hand hygiene, using disposable needles, discarding used needles into sharps containers) and recommending against acupuncture for those with conditions including neutropenia, thrombocytopenia, tumor involvement at the needling site, and other unstable medical conditions as determined by the acupuncturist and health care team, including oncologists.⁵⁵

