3.2 Inclusion Criteria

Subject must meet all the following applicable inclusion criteria to participate in this study:

1. Written informed consent and HIPAA authorization for release of personal health information. **NOTE:** HIPAA authorization may be included in the informed consent or obtained separately.

2. Age \geq 18 years at the time of consent
3. Subject has diagnosis of Multiple Myeloma (any stage)
4. Currently being treated with bortezomib or bortezomib-combination chemotherapy OR subjects who have discontinued bortezomib within the past 12 months but continue to have CIPN (even if they have started new therapy that could cause neuropathy)
5. ECOG Performance status of 0-3
6. Life expectancy of \geq 12 weeks
7. Subject-reported Neuropathy score of \geq 2
8. No planned hospital admission within the expected time frame of study participation. For potential participants with a transplant in their current MM treatment plan: Post-transplant subjects may enroll when recovered sufficiently from the transplant, i.e. platelets $>50 \times 10^3/\mu\text{L}$, ANC $> 0.5 \times 10^3/\mu\text{L}$, and ECOG performance status is 0-3.
9. As determined by the enrolling physician, ability of the subject to understand and comply with study procedures for the entire length of the study

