3.3 Exclusion Criteria

Subjects meeting any of the criteria below may not participate in the study:

1. Uncontrolled intercurrent illness/medical condition or psychiatric illness/social situations that would limit compliance with study requirements as determined by the investigator
2. Subjects with neuropathy pain as a result of any other cause other than chemotherapy
3. Subjects with needle phobia
4. Previous diagnosis of amyloidosis or POEMS syndrome
5. Documented local infection at or near the planned acupuncture sites (see Appendix A) as determined by the enrolling investigator
6. Subjects with metastatic involvement of the nervous system/active central nervous system disease
7. Plan to receive Healing Touch or Oncology Massage during study
8. Have received acupuncture within 30 days prior to enrollment

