5. STUDY PLAN

See Schema

This randomized, controlled trial is designed to evaluate the effect of acupuncture on CIPN, other symptoms, and potential opioid and concomitant medication sparing effects in comparison to standard of care management in MM subjects. Enrollment in this study should not affect subject care in any way. Subjects will not be reimbursed for study participation; however, the acupuncture treatments will be covered by the study and will be at no cost to the subject. This study will open as a single center study at LCI Morehead.

Potential participants with a transplant in their current MM treatment plan: Subjects may be enrolled in this study either prior to stem cell transplant or after they have completed their transplant. Subjects will be enrolled prior to transplant if they are able to complete the study prior to hospitalization for transplant. Subjects will be enrolled post-transplant if scheduling will not allow them to complete the study prior to hospitalization or transplant. Post-transplant

subjects may enroll when recovered sufficiently from the transplant, i.e. platelets $>50 \times 10^3/\mu\text{L}$, ANC $> 0.5 \times 10^3/\mu\text{L}$, and ECOG performance status is 0-3.

Subjects will be enrolled over approximately twelve months. Each enrolled subject will be on study for approximately 3 to 4 months.

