7.1.4 Acupuncture

The acupuncture procedure and specific acupoints will be performed in accordance with the Revised Standards for Reporting Interventions in Clinical Trials of Acupuncture (STRICTA) guidelines⁶⁷ in **Appendix A**. Acupuncture in this study will occur twice during weeks 1-2, then once weekly during weeks 3-10. During Week 1 and Week 2, if an acupuncture session is missed, it may be made up the following week (there will be 3 sessions that following week). During Weeks 3-10, no sessions will be made up if missed. The date of acupuncture sessions completed and acupoints received will be documented. Subjects may continue to receive acupuncture sessions per protocol even if bortezomib or bortezomib-combination treatment is discontinued. Subjects should continue per protocol acupuncture sessions even if their neuropathy resolves.

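### The protocol's background advises against acupuncture in neutropenia and thrombocytopenia, but its only platelet and ANC limits cover post-transplant subjects at entry, and no rule holds a session for low counts

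*Combined protocol and SAP*

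**What the plan says.** Section 1.1.7, which is background and cites a source, lists "recommending against acupuncture for those with conditions including neutropenia, thrombocytopenia" among the ways to lower acupuncture risk in cancer patients. It gives no cut-off and leaves the matter to clinical judgement, "as determined by the acupuncturist and health care team, including oncologists".

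The operative sections say the following.

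- **Entry, section 3.2.** Item 8 has the only numeric limits: "Post-transplant subjects may enroll when recovered sufficiently from the transplant, i.e. platelets" above 50 x 10^3/µL and ANC above 0.5 x 10^3/µL. The synopsis and section 5 repeat them. Item 4 admits subjects on active bortezomib or a bortezomib combination and sets no count condition.
- **Entry, section 5.** The pre-transplant route depends on timing only: "Subjects will be enrolled prior to transplant if they are able to complete the study prior to hospitalization for transplant".
- **Exclusions, section 3.3.** None of the eight names blood counts. Item 5 is a needling-safety exclusion: "Documented local infection at or near the planned acupuncture sites". Item 1 covers uncontrolled illness and psychiatric or social situations, and ends with "would limit compliance with study requirements as determined by the investigator".
- **Sessions, section 7.1.4, calendar footnote 2 and Appendix A.** There are visit windows, make-up rules and instructions on continuing, for example "Subjects should continue per protocol acupuncture sessions even if their neuropathy resolves". Appendix A item 7 assigns the fixed point set to every acupuncture subject at every session. No hold is written, and the calendar has no blood count.
- **Records, section 7.1.4.** "The date of acupuncture sessions completed and acupoints received will be documented". The reason for a single missed session is not mentioned.

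**The concern.** The protocol identifies low counts as a reason to advise against needling, and it follows bleeding, bruising and skin infection at the needling site as events of special interest (section 10.1.1). Yet it turns that advice into a rule for one subgroup at one moment, and words that rule as recovery from transplant. Followed as written, the protocol would let a subject on active bortezomib-combination therapy, or one enrolled before transplant, be randomized and needled whatever the latest count. A post-transplant subject who met the limits at entry could be needled later after counts had fallen.

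What is at stake is patient safety. A smaller matter is reporting: no field is dedicated to why a session was skipped, so the report may be unable to say how often low counts were the reason.

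**Working it through.** **1. The design figure, to show what is not at issue.** Inputs from section 11.2: two-sided Fisher's exact test, alpha 0.20, rates 0.10 and 0.35, 22 and 44 evaluable subjects. Exact enumeration gives power 0.817, which agrees with the stated minimum of 80%. Enrollment of 75 for 66 evaluable implies 1 − 66/75 = 12% not evaluable. Blood counts enter none of this.

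**2. Who has a written count condition.**

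| Subject | At entry | At later sessions |
|---|---|---|
| Post-transplant | Platelets >50, ANC >0.5 (x 10^3/µL) | None |
| Enrolled before transplant | None | None |
| On active bortezomib, no transplant in plan | None | None |
| Off bortezomib up to 12 months, no transplant in plan | None | None |

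The gap is therefore every subject other than post-transplant at entry, and every acupuncture subject afterwards.

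**3. Size of the gap.** The frequency of low counts, and of harm from them, is not in the documents and cannot be computed. The fixed set is 10 points (7 body, 3 ear) at each of 12 planned sessions. That describes exposure, not risk, and Appendix A item 2a leaves the number of insertions open.

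**4. Cost of an entry limit.** Number screened = 75 / (1 − f), where f is the share of otherwise eligible subjects failing the count. The values of f are assumptions.

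- f = 5%: 75/0.95 = 78.9, so 79 (4 extra)
- f = 10%: 75/0.90 = 83.3, so 84 (9 extra)
- f = 20%: 75/0.80 = 93.75, so 94 (19 extra)

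**5. Cost of a session hold.** Section 11.4 requires 9 of 12 sessions for the intervention-compliant population. Assume that a count stays in force for 28 days. Assume also that sessions fall on days 0, 3, 7 and 10, then weekly from day 14 (a Monday start, which footnote 1 allows, with Thursday as the second day).

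| Low count drawn | Later adequate count | Sessions held | Left of 12 | Compliant |
|---|---|---|---|---|
| Just after session 1 | None in 28 days | 6 (days 3, 7, 10, 14, 21, 28) | 6 | No |
| Just after session 1 | By day 21 | 4 (days 3, 7, 10, 14) | 8 | No |
| Weeks 3-10, between sessions | None in 28 days | 4 | 8 | No |
| Weeks 3-10, on a session day | None in 28 days | 5 | 7 | No |
| Weeks 3-10 | Within 21 days | 3 | 9 | Yes |

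In the first two rows the make-up rule does not help, because the make-up weeks are held as well. In Weeks 3-10 up to three holds keep a subject compliant, if no other session is missed.

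**6. Interaction with footnote 2.** In Weeks 3-10 visits may be at most 9 days apart. One held weekly session leaves about 14 days, so a hold would breach the window unless the text exempts it.

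**The case against.** The strongest reply is that section 1.1.7 supplies its own mechanism. It advises rather than prohibits, sets no threshold, and leaves the decision to the acupuncturist and the oncology team. The acupuncturists are accredited and have at least 8 years of experience (Appendix A item 5). The investigator may stop treatment (8.1) or remove a subject (8.2), and a local procedure on counts may exist under section 9.1. All of this stands, and it makes the gap smaller. It does not close it: sections 13.3 and 13.6 require adherence to the written procedures, and those give no count at which to stop.

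Several stronger readings are tempting, and the documents do not support them.

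- *The protocol contradicts itself.* It does not. Section 1.1.7 is background, and clinical judgement is consistent with it.
- *Most eligible subjects are unprotected.* The post-transplant share is not given.
- *Exclusion 1 cannot reach low counts.* The compliance clause may qualify only the psychiatric and social half of the item. If so, an uncontrolled medical condition is excludable in itself.
- *Subjects will be needled at any count.* The documents show that no limit is written, not that clinicians would ignore counts. Section 7.1.4 accepts missed sessions, so a clinician can skip one.
- *The report could never recover why sessions were skipped.* A long gap may be logged as a deviation (13.4), and reasons for stopping treatment are summarized (11.5.2). What is missing is a routine field for each session.

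The objection that a fix has costs of its own also stands. Holds in the twice-weekly phase are expensive, an entry rule needs a fallback when no recent count exists, and the item 8 values were not written as needling limits.

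**Conclusion.** The point holds as a patient-safety omission, minor to moderate. The protocol names a risk-reduction measure and puts it into operation only for post-transplant subjects at entry. The frequency is unknown, and section 1.1.7 calls serious events rare. There is no effect on the primary test, power or error rate.

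The conclusion rests on the text alone. The screening and hold figures rest on an assumed 5% to 20% failure rate, a 28-day window and the session days set out above. They size the remedy, not the harm.

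**What to change.** 1. **Section 3.2.** Apply the item 8 values to all subjects, using the latest routine-care count within a clinician-set window before randomization. If there is none, the treating oncologist confirms suitability, so no extra draw is mandated.
2. **Section 7.1.4 and footnote 2.** Hold a session when the latest routine-care count within the window is at or below either value, and resume when a later count is above both. If there is no recent count, the oncologist decides. Record the reason for each held session, and state that a hold does not breach the between-visit window. Cover a held first session too, because footnote 1 gives two weeks for it.
3. **Cut-offs.** The sponsor's clinicians should confirm the two values as needling limits. If a clinic policy on counts already exists, citing it in section 7.1.4 can replace item 2.

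The cost is a short amendment, one recorded field and a look at the medical record before each session. The downsides are some screen failures, fewer subjects in the intervention-compliant (sensitivity) population, and a lower delivered dose in the acupuncture arm. The last matters because section 1.2 expects higher doses to do better; its size cannot be computed from the documents. A prompt repeat count limits the loss, though in Weeks 1-2 even a repeat by day 21 may leave a subject at 8 of 12. Holds remove nobody from the evaluable population, which needs only baseline and Week 10 neuropathy scores (11.4).
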